6.3 Duration of Study and Visit Schedule

Each participant is engaged in the overall study for approximately 9 months as follows:

- Up to 15 days: Consent, screening and randomization.
- 24 weeks: Weekly research visits for 24 weeks; and active treatment, once inducted, up to week 24 post-randomization.
- 12 weeks: Follow-up, with visits at weeks 28 and 36 post-randomization.

7.0 STUDY POPULATION

Study participants are treatment-seeking heroin- and/or prescription opioid-dependent volunteers, without chronic pain requiring opioid therapy, who are willing to accept “agonist-based” or “antagonist-based” therapy. Randomization is stratified by (1) treatment site, and (2) baseline opioid use (high level use [≥ 6 bags {or equivalent} IV heroin/day] vs. all others [i.e., < 6 bags {or equivalent} IV heroin/day and other routes of administration or other opioids]).

7.1 Inclusion Criteria

1. Male or female;
2. 18 years of age and older;
3. Meet DSM-5 criteria for opioid-use disorder (heroin and/or prescription opioids);
4. Have used opioids other than as specifically prescribed within thirty days prior to consent;
5. Seeking treatment for opioid dependence and willing to accept “agonist-based” or “antagonist-based” therapy;
6. In good-enough general health, as determined by the study physician on the basis of medical history, review of systems, physical exam and laboratory assessments, to permit treatment with XR-NTX or BUP-NX;
7. Able to provide written informed consent;
8. Able to speak English sufficiently to understand the study procedures and provide written informed consent to participate in the study;
9. If female of childbearing potential, be willing to practice an effective method of birth control for the duration of participation in the study.

7.2 Exclusion Criteria

1. Serious medical, psychiatric or substance use disorder that, in the opinion of the study physician, would make study participation hazardous to the participant or compromise study findings or would prevent the participant from completing the study. Examples include:
 - (a) Disabling or terminal medical illness (e.g., uncompensated heart failure, cirrhosis or end-stage liver disease) as assessed by medical history, review of systems, physical exam and/or laboratory assessments;
 - (b) Severe, untreated or inadequately treated mental disorder (e.g., active psychosis, uncontrolled manic-depressive illness) as assessed by history and/or clinical interview;
 - (c) Current severe alcohol, benzodiazepine, or other depressant or sedative hypnotic use likely to require a complicated medical detoxification (routine alcohol and sedative detoxifications may be included);
2. LFTs (ALT, AST) greater than 5 times upper limit of normal;
3. Suicidal or homicidal ideation that requires immediate attention;
4. Known allergy or sensitivity to buprenorphine, naloxone, naltrexone, poly(lactide-co-glycolide), carboxymethylcellulose, or other components of the Vivitrol[®] diluent;
5. Maintenance on methadone at doses of 30mg or greater at the time of signing consent;
6. Presence of pain of sufficient severity as to require ongoing pain management with opioids;
7. Pending legal action or other reasons that might prevent an individual from completing the study;
8. If female, currently pregnant or breastfeeding, or planning on conception;

9. Body habitus that, in the judgment of the study physician, precludes safe intramuscular injection of XR-NTX (e.g., BMI>40, excess fat tissue over the buttocks, emaciation).

7.2.1 Special Populations to Consider

This study is likely to enroll persons involved in the criminal justice system, many of whom are expected to be in treatment at the CTPs conducting this study. The study will not recruit persons incarcerated/detained in a correctional facility, but will not exclude parolees, probationers, or persons in sentencing diversion or drug court programs who are enrolled at participating CTPs. Some of these subjects may be classified as prisoners per 45 CFR 46 Subpart C.

7.3 CTP Sites

This multi-site trial involves 8 CTPs that: (a) provide or partner with opioid detoxification services (inpatient/residential) which have the capacity to maintain participants opioid-free, (b) have the capacity to initiate participants onto XR-NTX or BUP-NX while they are still in an inpatient/residential setting, (c) have the capacity to maintain participants on XR-NTX or BUP-NX for the duration of 24-week trial, (d) have a sufficient flow of patients completing detoxification and who do not routinely receive long-term medication-assisted therapy as to provide a sufficient population of potential participants to achieve study enrollment goals, and (e) can provide a minimum level of outpatient care (at least one group and/or individual counseling session per week) for 24 weeks.

8.0 STUDY PROCEDURES

Refer to Figure 1 (Study Schema).

8.1 Recruitment and Screening (Phase 1)

Recruitment efforts will vary per site, and may broadly include CTP staff education and distribution of study materials, community or participant-level outreach and advertisements, and the encouragement of word-of-mouth referrals among CTP patient populations. During (or prior to) the first several days of an index admission, clinical and/or research staff will provide information about the study to interested, potential participants.

8.1.1 Informed Consent (Phase 1)

At any point candidates may begin the informed consent and screening procedures. The timing of consent and screening procedures is flexible, and allows CTPs to customize recruitment, screening, and randomization procedures to accommodate local conditions. Obtaining consent and baseline data early in the admission will allow a full accounting of persons interested in study enrollment but then not choosing to or not able to enroll (screen fails), while enrollment towards the end or just after detoxification will allow participants initially exposed to enrollment to reconsider and join the trial several days later. Candidates for the study are given a current local IRB-approved copy of the Informed Consent Form to read. Appropriately qualified and trained study personnel explain all aspects of the study in lay language and answer all of the study candidate's questions. Candidates who remain interested after receiving an explanation of the study are given a short informed consent quiz to test his/her understanding of the project, the purpose and procedures involved, and the voluntary nature of his/her participation. Those who cannot successfully answer quiz items have the study re-explained by research staff with a focus on aspects they did not understand. Those who demonstrate understanding of the study and voluntarily agree to participate are asked to sign the Informed Consent Form. Participants will not be administered any assessments or study procedures prior to signing informed consent. Participants are also asked to sign a release of medical records request to permit study staff to access CTP records relating to the index admission, primarily for the purpose of accessing clinical laboratory information (e.g., liver function tests) to eliminate repeat testing and speed randomization.

8.1.2 Detoxification

Guidelines for protocol-guided opioid detoxification (to be initiated after informed consent and depending on when in the detoxification process consent is obtained) are provided in the study MOP. Data on the detoxification, including number of days on the unit and medications received, are collected.

8.1.3 Screening and Baseline Assessments (Phase 1)

Screening and baseline assessments are detailed in Section 11 and capture participant demographic, medical, psychiatric, drug use, and treatment history, quality of life and current health status, in addition to blood and urine testing. These assessments confirm eligibility/ineligibility. Screening may take place at any time during Phase 1. LFTs performed within 4 weeks prior to randomization (i.e., drawn as part of usual care) are acceptable. If LFT results are available at screening, and participants meet all eligibility criteria, randomization may proceed. Otherwise, final eligibility is determined upon confirmation of LFTs.

8.2 Randomization (Phase 1, Day 0)

Randomization follows final confirmation of eligibility.

While the timing of randomization can be variable, it is expected that each randomized participant will initiate his or her assigned treatment. Success in initiating assigned treatment is tracked.

8.3 Stratified Randomization

A restricted randomization plan is used with centralized, automated, randomized block assignments. Randomization is stratified by two factors, site and pre-detoxification level of opioid use. While there are important and otherwise uncharacterized differences between sites – including state and local treatment service environments, opioid misuse epidemiology, and patient-level customs regarding treatment, medications, and clinical trial participation – the level of heroin and other opioid use will likely be an important independent predictor of treatment retention and rates of negative urines as has been demonstrated in recent analysis of naltrexone opioid trials.⁶⁰⁻⁶² The level of opioid use at treatment entry is a binary classification, operationally defined as 6 or more bags (or equivalent) IV heroin per day (≥ 6 bags/day) over the 7 days prior to entry into the treatment program versus less than 6 bags (or equivalent) IV heroin per day (< 6 bags/day) or other routes of administration or other opioids.

Timing of the randomization is important to execution of the design and may also be an important prognostic variable. All cases are classified into one of three groups at the time of randomization, those:

- (a) randomized within 24 hours of last (licit or illicit) opioid use;
- (b) randomized between 24 and 72 hours following last (licit or illicit) opioid use;
- (c) randomized more than 72 hours following last (licit or illicit) opioid use.

Each of these groups represents different clinical scenarios commonly encountered in CTN CTPs. Group (a) represents early decision-making, at such a time as to avoid unnecessary detoxification for those choosing BUP-NX. For group (b), decision-making occurs later during detoxification, but while participants still need to surmount the detoxification hurdle to begin XR-NTX. Group (c) includes participants who can be readily inducted onto either medication.

Individuals in groups (a) and (b) comprise the early cases used in the decision rule assessment after 100 of these participants had entered.

8.4 Induction (Phase 2)

Following randomization, participants are inducted onto their assigned pharmacotherapy. Guidelines for detoxification and induction onto XR-NTX or BUP-NX are provided in the study MOP.

XR-NTX assignment: participants randomized to XR-NTX must complete/have completed a recent opioid detoxification, be ≥ 3 days removed from the last dose of opioid agonist (heroin, prescription opioids, methadone or buprenorphine), have a urine toxicology negative for the extended opioid spectrum, including methadone and buprenorphine, and have a negative naloxone challenge.

BUP-NX assignment: a) participants randomized during a buprenorphine-based detoxification will continue on buprenorphine, now as a daily maintenance dose. BUP-NX will be titrated over 1-3 days to a maintenance dose range of 8-24mg/day. Lower doses and doses up to 32mg/day may be prescribed with the approval of the site PI and Study Physician; b) participants randomized during a methadone-based detoxification will discontinue methadone, and be

inducted onto BUP-NX no less than 24 hours following the last methadone dose, after withdrawal symptoms have clearly emerged; c) participants randomized during a non-opioid-based detoxification or after completing a buprenorphine- or methadone-based detoxification may be inducted onto BUP-NX immediately or after a sufficient delay since last methadone dose.

8.5 Study Treatments (Phase 3)

Table 1: Treatment Visit Schedule

Study Week	-1	0	1	2	3	4	5	6	7	8	9	10	11	12	13	14	15	16	17	18	19	20	21	22	23	24
Medical Management Visits (both arms)		x	x	x	x	x		x		x		x		x		x		x				x				x
XR-NTX Administration			x*	x*	Approximately every 4 weeks, with final injection occurring no later than week 22.																					
BUP-NX Dispensing		x	x	x	x	x		x		x		x		x		x		x				x				x ⁻

x*=the initial XR-NTX dose will depend on the length of time needed to complete detoxification and begin XR-NTX treatment; x⁻ = for BUP-NX taper where indicated

A. Medical Management: Both Arms

Both groups receive Medical Management (MM) clinical support from the same study clinicians (e.g., MD, DO, PA, NP, RN; working within the scope of their local licensure, clinical privileges and/or scope of practice) in unblinded fashion. MM is adapted from several recent studies of NTX, XR-NTX and BUP-NX, including the NIAAA COMBINE study⁶³, Krupitsky et al.⁸, and CTN-0030 (POATS).⁵⁷ Briefly, MM sessions focus on establishing and maintaining patient-clinician rapport and partnership, education surrounding opioid addiction and treatment, establishing and maintaining a plan for XR-NTX or BUP-NX medication adherence, advice and encouragement to maintain abstinence, monitoring medication side effects and dose adjustments, and support for ancillary treatment, including weekly psychosocial counseling, 12-step involvement, and further community-based treatment. MM also provides guidelines for assessment and management of relapse in both arms. In contrast to studies specifically analyzing the effect of a trial's psychosocial interventions (i.e., the COMBINE trial or CTN-0030, POATS), and in keeping with a pragmatic, community-based comparative effectiveness trial, MM is broadly guided by provider training prior to study start and regular MM provider calls, a common progress note and the MM MOP, but is not subject to rigorous quality assurance procedures (i.e., audiotaping, manualization and QA audits). The study clinician assesses concomitant medications at each medical management visit. As this is not an IND study, and both medications are FDA approved for opioid dependence, the study data capture system does not include a concomitant medication case report form. MM visit schedules are the same for both arms, initially weekly (weeks 0-4), then every two weeks (weeks 4-16), and finally every four weeks (weeks 16, 20, 24). XR-NTX is injected at the MM visit approximately every 4 weeks with the final injection occurring no later than week 22. BUP-NX is dispensed at each MM visit through week 20. For all participants a final MM visit takes place on week 24 although no medication is dispensed (except for BUP-NX taper where this is indicated).

B. Psychosocial Counseling: Both Arms

Psychosocial counseling consists of outpatient counseling provided at the CTP. Selected sites agree to provide at least a minimum level of outpatient care that consists of at least one group and/or individual counseling session per week for up to 24 weeks. Data is collected from the clinic record or from the participant on counseling sessions attended. Participation in counseling sessions is voluntary. Failure to attend counseling sessions will not be considered to be a reason to be excluded from the trial.

8.5.1 XR-NTX Group

Prior to the naloxone challenge, participants randomized to XR-NTX must complete/have completed a recent opioid detoxification, be ≥ 3 days removed from the last dose of opioid agonist (heroin, prescription opioids, methadone or buprenorphine) and have a urine toxicology negative for all opioids, including buprenorphine. If initial UDS is positive, UDS is repeated daily until negative. Only then will the naloxone challenge take place.

8.5.1.1 XR-NTX Injections

Following a negative naloxone challenge (see MOP), XR-NTX monthly injections begin. XR-NTX (4cc, ~380mg of naltrexone base) is administered approximately every four weeks (with the final injection occurring no later than week 22), in the form of Vivitrol[®] which is obtained by NIDA or the NIDA contractor for distribution to the sites. XR-NTX injections may take place <4 weeks apart if there is clinical concern about non-adherence (participant is inconsistent in attending scheduled visits) or if clinical observation is that opioid craving and/or use re-emerge during the 4th week after the last injection; however, time between injections must always be at least 21 days. XR-NTX is administered by intramuscular injection to the buttocks (alternating sides) according to the injection preparation and administration procedures specified in the Vivitrol[®] product package insert (see Appendix C). These procedures are designed to minimize the risk of injection site reactions.

8.5.1.2 Ancillary Medications

Participants who experience withdrawal symptoms, sleeplessness, and/or depressive symptoms may be treated with ancillary medications (see guidelines in the study MOP). Depression is common in opioid-dependent patients and may adversely affect prognosis of naltrexone treatment.⁶⁰ Participants who show depressive symptoms may be treated with antidepressants and/or referred for psychiatric evaluation and treatment. In general, psychiatric or medical problems emerging during the study treatment period are handled by the CTP according to their usual practices for treatment and referral.

8.5.1.3 Handling of Missed XR-NTX Doses, Lapses, and Relapses

Use of illicit opioids presents different concerns in the management of patients receiving XR-NTX maintenance, compared to those receiving BUP-NX. Because of the long duration of action of XR-NTX (full blockade out to 5 weeks after the last injection¹⁷), a grace period of 7-21 days can be expected during which the injection can be rescheduled, provided the participant has not relapsed and become re-dependent. If the participant misses a scheduled injection and does not otherwise meet the primary outcome of relapse, XR-NTX may then be continued following a negative naloxone challenge (if clinically indicated) up to 21 days after a missed dose (49 days post prior injection; see MOP).

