8.5.3 Dispensing of XR-NTX and BUP-NX

Study medications (XR-NTX and BUP-NX) are provided by the study at no cost to the participant. XR-NTX is administered in-clinic at induction and approximately every four weeks with the final injection occurring no later than week 22. BUP-NX is dispensed to participants at induction and at treatment weeks 1, 2, 3, 4, 6, 8, 10, 12, 14, 16, and 20. Medication may be dispensed more frequently at the discretion of the study clinician. In addition, for participants receiving BUP-NX who are discontinued, who do not wish to continue, or for whom community resources to continue are not available, the study may dispense sufficient BUP-NX for up to a two-week taper beginning at any time during treatment or beginning at the week 24 visit. BUP-NX dose adjustments or emergency medication replacement between visits are allowed and will necessitate as-needed treatment and medication-dispensing visits. The clinical team may extend the window for medication administration or dispensing by up to three weeks if (a) the participant is abstinent (both self-report and urine are negative), (b) can restart the originally assigned medication, and (c) the treatment lapse is scheduled (i.e., the participant has provided a credible reason for the lapse and remains in contact with the study team).

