13.5.3 IND Requirements

Medications to be used in this study will be used in accordance with their approved labeling and therefore there is no plan to submit an IND application.

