4. CONTRAINDICATIONS

VIVITROL is contraindicated in:

- Patients receiving opioid analgesics [see *Warnings and Precautions (5.3)*].
- Patients with current physiologic opioid dependence [see *Warnings and Precautions (5.3)*].
- Patients in acute opioid withdrawal [see *Warnings and Precautions (5.3)*].
- Any individual who has failed the naloxone challenge test or has a positive urine screen for opioids [see *Warnings and Precautions (5.3)*].
- Patients who have previously exhibited hypersensitivity to naltrexone, PLG, carboxymethylcellulose, or any other components of the diluent [see *Warnings and Precautions (5.8)*].

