5 WARNINGS AND PRECAUTIONS

5.1 Vulnerability to Opioid Overdose

After opioid detoxification, patients are likely to have reduced tolerance to opioids. VIVITROL blocks the effects of exogenous opioids for approximately 28 days after administration. However, as the blockade wanes and eventually dissipates completely, patients who have been treated with VIVITROL may respond to lower doses of opioids than previously used, just as they would have shortly after completing detoxification. This could result in potentially life-threatening opioid intoxication (respiratory compromise or arrest, circulatory collapse, etc.) if the patient uses previously tolerated doses of opioids. Cases of opioid overdose with fatal outcomes have been reported in patients who used opioids at the end of a dosing interval, after missing a scheduled dose, or after discontinuing treatment.

Patients should be alerted that they may be more sensitive to opioids, even at lower doses, after VIVITROL treatment is discontinued, especially at the end of a dosing interval (i.e., near the end of the month that VIVITROL was administered), or after a dose of VIVITROL is missed. It is important that patients inform family members and the people closest to the patient of this increased sensitivity to opioids and the risk of overdose [see *Patient Counseling Information (17)*].

There is also the possibility that a patient who is treated with VIVITROL could overcome the opioid blockade effect of VIVITROL. Although VIVITROL is a potent antagonist with a prolonged pharmacological effect, the blockade produced by VIVITROL is surmountable. The

plasma concentration of exogenous opioids attained immediately following their acute administration may be sufficient to overcome the competitive receptor blockade. This poses a potential risk to individuals who attempt, on their own, to overcome the blockade by administering large amounts of exogenous opioids. Any attempt by a patient to overcome the antagonism by taking opioids is especially dangerous and may lead to life-threatening opioid intoxication or fatal overdose. Patients should be told of the serious consequences of trying to overcome the opioid blockade [see Patient Counseling Information (17)].

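### Protocol 8.5.1.3, Protocol 8.5.3 and the appended label state different conditions for giving a late XR-NTX injection, and the operative sentence of 8.5.1.3 admits urine-positive participants whom the label contraindicates

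*Protocol*

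**What the plan says.** Under Protocol 8.5.1.1, XR-NTX "is administered approximately every four weeks". Three places then bear on an injection that is late.

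- **Protocol 8.5.1.3 (XR-NTX only).** If a scheduled injection is missed and the relapse endpoint is not otherwise met, "XR-NTX may then be continued following a negative naloxone challenge (if clinically indicated) up to 21 days after a missed dose". The outer limit is given as "49 days post prior injection; see MOP". The sentence before it describes a 7 to 21 day grace period, subject to the participant not having relapsed and become dependent again, and rests this on full blockade lasting 5 weeks.
- **Protocol 8.5.3 (administration or dispensing, so both arms).** The clinical team may extend the window "by up to three weeks if (a) the participant is abstinent (both self-report and urine are negative"), the assigned drug can be restarted, and "the treatment lapse is scheduled", meaning that a credible reason was given and contact is kept.
- **Appendix C (label).** Section 4 lists as contraindicated: "Any individual who has failed the naloxone challenge test or has a positive urine screen for opioids". Section 2.1 says that patients reinitiating should be free of opioids at dosing. Section 5.1 says: "VIVITROL blocks the effects of exogenous opioids for approximately 28 days after administration".

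Protocol 13.5.3 ties the study to the label: "Medications to be used in this study will be used in accordance with their approved labeling". It gives this as the reason for not planning an IND application. Protocol 9.1 defines relapse as four consecutive opioid use weeks or seven consecutive days of self-reported use.

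**The concern.** Sections 8.5.1.3 and 8.5.3 govern a delay of the same length under different conditions, and neither refers to the other. Section 8.5.1.3 uses the primary endpoint as its screen for drug use. That endpoint was built to detect sustained relapse, and a participant can have several opioid-positive weeks without meeting it. Followed as written, the operative sentence therefore reaches participants with a positive opioid urine, whom the appended label contraindicates.

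The stake is participant safety. Label section 5.3 warns that withdrawal precipitated by an antagonist in an opioid-dependent patient can be severe enough to need hospital admission. A secondary matter is consistency: two sites reading the protocol in good faith could handle the same late participant differently.

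**Working it through.** **The time limit.** Inputs: a four-week interval (8.5.1.1), 21 days of lateness (8.5.1.3) and three weeks of extension (8.5.3).

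- 8.5.1.3: 4 × 7 + 21 = 49 days, which reproduces the stated figure.
- 8.5.3, on a four-week schedule: 28 + 3 × 7 = 49 days.

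The limits agree, so the conflict lies in the conditions.

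**What not relapsed allows.** Criterion (a) needs 4 consecutive use weeks, so 3 do not meet it. Criterion (b) needs 7 consecutive self-reported days, so 6 do not meet it. A participant with three opioid-positive weeks and no run of seven reported days has not relapsed. The 21 days of permitted lateness equal 21 / 7 = 3 weeks.

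**The conditions side by side.** Take a participant who has not relapsed, is within 49 days, could restart the drug, and had a negative result on any naloxone challenge done. An abstinent participant with a positive urine is impossible by the definition in 8.5.3, which leaves six cases:

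| Abstinent | Lapse scheduled | Urine at injection | Operative sentence of 8.5.1.3 met | Conditions of 8.5.3 met | Contraindicated on urine (label section 4) |
|---|---|---|---|---|---|
| no | no | negative | yes | no | no |
| no | no | positive | yes | no | **yes** |
| no | yes | negative | yes | no | no |
| no | yes | positive | yes | no | **yes** |
| yes | no | negative | yes | no | no |
| yes | yes | negative | yes | yes | no |

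The operative sentence of 8.5.1.3 is met in 6 of 6 and 8.5.3 in 1 of 6. The label's urine contraindication applies in 2 of 6. These count combinations of conditions; they are not patient frequencies. The re-dependence clause of 8.5.1.3 is not applied in the table, because the operative sentence does not repeat it and no test for it is named.

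**Comparison with the first injection.** Protocol 8.4 and 8.5.1 require at least 3 days since the last opioid agonist, a negative urine and a negative naloxone challenge. For the late injection, 8.5.1.3 mentions only the last of these, and conditionally.

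**Blockade duration.** Section 8.5.1.3 gives 5 × 7 = 35 days; label section 5.1 gives about 28. Day 49 is 49 − 35 = 14 days beyond the first and 49 − 28 = 21 days beyond the second. The lower end of the grace period, 28 + 7 = 35 days, matches the 5 weeks; the upper end does not.

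**The case against.** The strongest reply is that the two sections have different scopes. Section 8.5.3 is permissive and its third condition marks it as the route for planned absences, while 8.5.1.3 covers missed injections. A reader might infer that 8.5.3 bars an unscheduled or non-abstinent participant. The text does not say so: such a case falls outside 8.5.3, and the grounds for stopping medication in Protocol 10.1 do not include an unscheduled lapse. This part of the reply stands. It does not reach the label conflict, and it leaves unplanned lapses under the looser conditions.

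Second, 8.5.1.3 is silent on urine and does not direct injection on a positive result. Its re-dependence clause, a challenge where indicated, the safety stop in 10.1 and the commitment in 13.5.3 could together keep a clinician within the label. Weekly urine screens (11.4.2) mean a result will often be in hand. That is fair, but the clinician has to supply the condition, since the section does not state it, and a positive urine is not the same thing as re-dependence.

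Third, the label itself advises giving a missed dose at the earliest opportunity with no day limit (section 2), and calls the naloxone challenge only possibly helpful (section 5.3). So a reader who infers that day 49, or a conditional challenge, breaches the label goes too far. Label section 2.1 is also headed for patients who had discontinued, and a late injection may not count as reinitiation. The contraindication in section 4 carries no such limit.

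Fourth, a reader might infer that the arms restart under unequal rules and that this biases the primary comparison. Section 8.5.1.3 does give XR-NTX a route with no BUP-NX counterpart. But it acknowledges that illicit use raises different concerns in the two arms, 8.5.2.3 lets the BUP-NX dose be titrated in response to use, and 8.5.3 allows as-needed dispensing. Nothing in the documents permits an estimate of any effect on the hazard ratio.

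Finally, 8.5.1.3 defers to the MOP, which is not among the documents and may settle part of this.

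**Conclusion.** The point holds as a conflict between written conditions. Section 8.5.1.3 contains two different tests, neither with a urine condition; 8.5.3 sets stricter conditions for the same delay without stating its scope; and the label that 13.5.3 adopts contraindicates the urine-positive participant whom the operative sentence of 8.5.1.3 admits. That last conflict covers two of the six cases and remains even if 8.5.3 is confined to planned absences. The differing blockade durations are a lesser inconsistency.

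This rests on reading the operative sentence as written, on the urine being positive at the time of injection, and on the MOP not already resolving the matter. How many participants are affected cannot be derived from the documents. No sample size, power or significance level changes, and no bias in the primary comparison is shown.

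**What to change.** The sponsor's medical team should reconcile Protocol 8.5.1.3, 8.5.3 and 13.5.3 with Appendix C label sections 2.1 and 4, after checking the MOP, into one stated set of conditions for resuming XR-NTX after a late injection. The revised text should:

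- use a single test in place of the two in 8.5.1.3;
- say whether 8.5.3 covers only scheduled lapses and how it relates to 8.5.1.3;
- say what applies to a late BUP-NX restart;
- reconcile the blockade durations.

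Which clinical conditions should stand is for the medical team; none is proposed here.

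The cost is a protocol and MOP clarification and a memo to sites, with no new visits or staff. Injection intervals (SAP Appendix A, Table 12) and weekly urine results are already collected, so the number of late injections, and of those given near a positive urine, could be described from existing data.
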